2.4 CHIVITT

This protocol will describe the general conduct of the CHIVITT, wherein we will estimate the relative contribution of aerosol inhalation (airborne), spray deposition (large droplet), and touch (contact-fomite) transmission on the spread of influenza, by determining the secondary attack rate (SAR) of influenza among uninfected volunteers (Recipients) who closely interact with naturally influenza-infected index

cases (Donors). The close interactions are designed to mimic real-world potential exposures to influenza. To identify the dominant mode of transmission, various interventions will be employed. The exposure room environment can be tuned to a low ventilation minimal filtration environment or a high ventilation, filtration, and air disinfection environment. The residential and common room environment may be supplemented with in-room air filtration and/or germicidal UV air disinfection to achieve high air hygiene conditions to block inhalation of infectious aerosols. Transmission via spray deposition may be blocked by face shield interventions. Touch (contact-fomite) transmission may be blocked through strict hand hygiene and surface cleaning protocols. Aerosol inhalation transmission may be further reduced by the donning of face masks. The determination of SAR in Recipients will be performed through a standardized procedure of collected respiratory specimens and daily symptom surveys. The monitoring and management of influenza illness will be conducted to ensure the welfare of all study participants.

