Pop-Up Kiosks. CLIA-waived rapid flu tests will be administered at “pop-up kiosks” on campuses or other locations thought to have a high likelihood of yielding individuals with positive flu tests. Kiosks will be staffed by trained study personnel. Visitors to the kiosk who want to be tested will self-swab, provide their email address, and answer questions about fever, cough, and sore throat. Trained study personnel will perform the rapid flu test and link the test to the visitor’s email address. Study recruitment fliers will be distributed. Individuals who get tested will receive an information sheet describing the risks and benefits of the rapid test, along with study materials. These settings where healthy students, families and/or other adults congregate (such as dormitories, student lounges, barber shops) will allow investigators to raise awareness of the study, provide the means for no-cost tests and improve the chances of enrolling individuals with the influenza very early in the course of their disease.

Lord Baltimore Hotel – We will provide CLIA-waived flu testing kiosk at the Lord Baltimore Hotel during the quarantine CHIVITT to facilitate identifying eligible donor volunteers. These individuals will have heard about the study via social media, fliers, or word of mouth, and have ILI but not been tested.

In these situations, they can obtain a flu test at the Lord Baltimore Hotel during periods when we are recruiting Donors.

Recipient Registry - individuals who are enrolled in the EMIT-2 Recipient Registry (HP-00097730), may be provided FDA approved home influenza rapid test kits during their screening or follow-up clinic visits if test kits are available. (This will be described in the Recipient Registry Protocol.) If they contract influenza-like illness during a CHIVITT donor recruitment, they can test themselves and volunteer as a donor if they are available and otherwise eligible.

For all potential Donors, a review of available electronic medical records may be necessary to assess for the presence of exclusion criteria prior to formal signed informed consent—this would require IRB approval to waive the HIPAA authorization to obtain identifiable private information for this pre-screening process, as it would not be practicable to conduct this research without the waiver.

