9 OUTCOMES AND DATA ANALYSIS

9.1 Primary Outcome Measure – Attack Rate of Influenza

The SAR of influenza infection will consist of virological confirmation, symptomatic infection, or serological evidence of an influenza infection.

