9.1.1 Viral Confirmation of Influenza Infection

BioFire Respiratory Panel. This CLIA-approved, commercially available molecular diagnostic test will be the primary means for determining influenza infection. The test result will be used for the day-to-day management and decision-making process for the care of study participants.

Cepheid 4-Plex. This CLIA-waived, commercially available molecular diagnostic test (which runs the Xpert® Xpress SARS-CoV-2/Flu/RSV assay) can be a satisfactory alternative means for determining influenza infection from the BioFire Respiratory Panel.

Qualitative RT-PCR. This research diagnostic test will be used as a secondary means for determining influenza infection. The test result may not be available for day-to-day decisions and the test may be performed in batched analysis.

Quantitative RT-PCR. This research diagnostic test will be used as another secondary means for the characterization of influenza infection. Peak viral shedding will be calculated for each subject as the maximum shedding during their CHIVITT participation period. Total viral shedding will be calculated with an area under the curve (AUC) with study day on the x-axis and shedding on the y-axis. The test result may not be available for day-to-day decisions and the test may be performed in batched analysis.

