9.2 Sample Size Considerations

We estimate effect sizes of interest based on an expected SAR of 25% and two alternate hypotheses that: a) long-range aerosol transmission accounts for 75% of transmission and b) contact, fomite, and spray-borne transmission account for 60% transmission. These hypotheses are essentially attributable fractions, not the expected effect size of the interventions. The interventions, unfortunately, cannot cleanly block one mode without impacting transmission via other modes. Therefore, we derived the estimated effect sizes for the interventions by analysis of planned interventions and their impact on each mode of transmission. It is assumed that hand hygiene and face shield is 100% effective for contact and spray-borne transmission and the effectiveness for short-range aerosols is based on the work of Lindsley⁵ and Bischoff⁶. The air hygiene (ventilation, filtration, and germicidal UV light) intervention will be designed to be 100% effective against long-range aerosol transmission using a validated computational model of these systems, to be developed by Research Project 2 of the EMIT-2 U19 Project, to achieve the equivalent of > 60 ACH. However, air hygiene interventions are relatively less effective against short-range aerosol transmission.

Because of incomplete blockage of aerosol transmission by air sanitation and partial blockage of short-range transmission by the face shields, we assume marginal effect size of 79% reduction in the observed SAR. To compute power, we use one-sided alternatives because we do not expect that either intervention is capable of increasing transmission. Given a sample size of 54 in an intervention group, we will have 84% power to detect the intervention effect with an alpha level of 5%.

For power to detect an effect of contact, fomite, and spray-borne transmission, we assume a marginal effect size of 76% reduction in observed SAR. Given a sample size of 63 in an intervention group, we will have 84% power to reject the null hypothesis of no effect with the hand hygiene and face shield.

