To protect privacy, the NIH has provided a Certificate of Confidentiality, CoC. With this CoC, the participating sites cannot be forced to release information that may identify the participant, even by a court subpoena, in any federal, state, or local civil, criminal, administrative, legislative, or other proceedings. The participating sites will use the CoC to resist any demands for information that would identify the participant, except as explained below.

The CoC cannot be used to resist a demand for information from personnel of the United States Government that is used for auditing or evaluation of federally funded projects, like this study or local laws, such as for reporting of communicable diseases.

A CoC does not prevent the participant from voluntarily releasing information about themselves or their involvement in this research. If any person or agency obtains a written consent to receive study information, then the participating sites may not use the CoC to withhold that information.

The CoC does not prevent the participating sites from reporting without the participant's consent, information that would identify the subject as a participant in the study regarding matters that must be legally reported including child and elder abuse, sexual abuse, or wanting to harm themselves or others.

Hotel staff will be providing services as per their standard duties and are instructed to maintain confidentiality as per the standards of the hotel industry. There will be no further control or oversight from the study team over the hotel staff with regards to assurances of confidentiality. Nonetheless, any breaches of confidentiality will be immediately brought to the attention of hotel executives and supervisors to minimize further occurrences.

Electronic data, photo, and video recordings are intended to be collected and stored using secure and password protected means, as described in [Section 2.5.1](#). Participants and the IRB will be informed should there be breaches in confidentiality with these forms of data.

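### The primary endpoint does not link a Recipient's influenza to a Donor, so infections from other sources, mainly through the one-month serology, can count as secondary attacks

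*Protocol*

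**What the plan says.** Section 2.4 describes the trial as "determining the secondary attack rate (SAR) of influenza among uninfected volunteers (Recipients) who closely interact with naturally influenza-infected index" cases, that is, Donors. Section 2.3 likewise treats secondary infections as transmissions from Donors to exposed Recipients.

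Section 9.1 defines the primary outcome: "The SAR of influenza infection will consist of virological confirmation, symptomatic infection, or serological evidence of an influenza infection".

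- **Virology (9.1.1).** Of the BioFire panel it says: "This CLIA-approved, commercially available molecular diagnostic test will be the primary means for determining influenza infection". No comparison with a Donor's virus is described.
- **Serology (9.1.3).** The criteria are a 4-fold or greater HAI rise from baseline, or an HAI titre of at least 40 one month after the CHIVITT. No strain is named. Under 8.1.8 the blood is drawn 3 to 5 weeks after discharge.
- **Operational use (6.4).** A Recipient with laboratory-confirmed influenza is a countable SAR, again without a Donor link.

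Donor-strain matching appears in section 4, where it concerns selecting susceptible Recipients, not the outcome.

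Section 9.2 plans on a control SAR of 25%. For air hygiene: "we assume marginal effect size of 79% reduction in the observed SAR". For hand hygiene and face shield: "we assume a marginal effect size of 76% reduction in observed SAR". Each is given 84% power, with 54 and 63 in an intervention group.

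**The concern.** The aim is transmission from Donors; the counting rule is any influenza. Followed as written, a Recipient infected with a subtype that no Donor carried is a primary event.

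Infections from elsewhere should not depend on the shield or the air condition in the exposure room. They would add about the same absolute risk to both sides of each contrast and shrink both relative reductions. Those reductions are how the trial apportions transmission between routes, so the primary objective is affected as well as the power. The intervention groups are expected to yield only three or four infections each, so a few stray cases would be visible in the result.

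**Working it through.** **1. Which routes are open**

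Safeguards in the protocol: multiplex test at admission (4.1), two-day run-in (6.1) against a stated 24 to 48 hour incubation (2.5.1), and private rooms with no guests and no free movement in or out (6.4).

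| Route | Covered by the safeguards? |
|---|---|
| Serology 3 to 5 weeks after discharge (8.1.8, 9.1.3), from cohorts timed at the local influenza peak (6) | No. Recipients have been back in the community for weeks |
| Infection acquired before admission that becomes detectable after two negative days, while daily tests may be paused until the first Donor exposure (8.1.3) | Partly. It would first be found after exposure and counted. Section 6.9 itself allows for late-onset, long-latency infection |
| Recipients joining mid-quarantine (6, 6.3) | Partly. The admission test applies; no run-in is stated specifically for late entrants |

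**2. The plan's own power figure**

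Inputs from 9.2: control risk 25%; one-sided alpha 5%; air hygiene risk 0.25 × (1 − 0.79) = 5.25%; shield risk 0.25 × (1 − 0.76) = 6.0%. The comparator size is not stated, so equal arms are assumed.

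Power = Φ[(d − 1/n − 1.645·SE0) / SE1], where d is the risk difference, SE0 the pooled and SE1 the unpooled standard error.

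For n = 54:
- d = 0.1975 and 1/n = 0.0185
- SE0 = √(0.15125 × 0.84875 × 2/54) = 0.0690
- SE1 = √((0.25 × 0.75 + 0.0525 × 0.9475)/54) = 0.0663
- Φ(0.989) = **83.9%**, which reproduces the stated 84%

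For n = 63 the same form gives 86.3%, not 84%. The air hygiene figure is therefore the one to rely on.

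**3. Adding a background risk b to both arms**

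The documents give no b, so a range is shown. Observed risk = 1 − (1 − p)(1 − b).

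Example, b = 5%: control 1 − 0.75 × 0.95 = 28.75%; air hygiene 1 − 0.9475 × 0.95 = 9.99%; observed reduction 1 − 9.99/28.75 = 65%.

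| b (assumed) | Air reduction | Power, n=54 | Shield reduction | Power, n=63 |
|---|---|---|---|---|
| 0 | 79% | 83.9% | 76% | 86.3% |
| 1% | 76% | 81.5% | 73% | 84.2% |
| 2% | 73% | 79.2% | 70% | 82.0% |
| 3% | 70% | 76.9% | 68% | 79.9% |
| 5% | 65% | 72.4% | 63% | 75.7% |

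**4. If the 25% already contains b**

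Donor-derived control risk is then q = 1 − 0.75/(1 − b). At b = 5%, q = 21.05%, the air hygiene group is observed at 9.2%, the reduction is 63%, and power at n = 54 is 61.3% (64.7% for the shield at n = 63). At b = 2% the powers are 75.6% and 78.7%.

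**5. Event counts**

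Expected intervention-group infections are 54 × 0.0525 = 2.8 and 63 × 0.06 = 3.8. One unrelated case, if it occurred, would add 1/2.835 = 35% or 1/3.78 = 26%.

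**The case against.** The Donor link is the declared intent of 2.3 and 2.4, and attribution of cases may be detailed in the SAP or manual of procedures, which are not at hand. That softens the point but does not dispose of it. The protocol itself fixes the primary endpoint, and 9.1 and 6.4 count without the link.

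The safeguards during quarantine are substantial, and importation during the stay is probably uncommon. That stands. It does not help with blood drawn weeks after discharge.

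Section 9.2 calls its reductions observed ones, which might suggest that dilution is already included. The reasons it gives concern only how completely each intervention blocks each route; background infection is not among them.

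A reader might infer more exposure inside the hotel than the documents show. Section 3.1 provides a flu-test kiosk there for untested people ("These individuals will have heard about the study via social media, fliers, or word of mouth, and have ILI but not been tested"), and 10.3 says "Hotel staff will be providing services as per their standard duties". Neither passage describes contact or shared air with confined Recipients, and the second concerns confidentiality. They do not establish a source of infection.

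A reader might also take the dilution as established, or expect matching to restore the b = 0 row. The documents support neither. The rate is assumed, at 1% the loss is small, and a community infection of the Donors' own subtype would pass a match.

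**Conclusion.** The point holds as a gap in the endpoint rule. As written, 9.1 to 9.1.3 can count infections that did not come from a Donor, and the one-month serology is the clearest way in. If such infections are equally frequent in both arms, both reductions are biased toward zero. At an assumed 1% to 5% background, 79% becomes 76% to 65%, 76% becomes 73% to 63%, and power at n = 54 falls by 2.4 to 11.5 points. The loss is larger if the 25% already includes the background. These figures rest on equal arms, no clustering and a background rate that the documents do not supply. They show sensitivity; they are not a forecast. The change is worth making because it is cheap and, in an open study with few expected events, an exclusion rule written after results are known would look selective.

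**What to change.** Amend 9.1 as follows.

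- **Virological events.** Count an event as primary only if its type/subtype is not discordant with every infectious participant (a Donor, or a Recipient infected within the cohort) with whom the Recipient shared a logged exposure event before the positive sample.
- **Serological events.** Read them only against that cohort's Donor strain(s).
- **Discordant infections.** Report them separately.
- **Sensitivity analyses.** Give all-influenza SAR, and SAR restricted to virologically confirmed infection during quarantine.
- **Untypable samples.** Keep them in the primary count unless shown to be discordant.
- **Symptom-only events.** State how they are handled, since there is no virus to compare.

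The cost is one endpoint rule. Donors and Recipients are already swabbed at admission and daily apart from the permitted pause (8.1.1, 8.1.3), exposure-event attendance is logged (8.1.2), and strain-specific titres are planned (8.2). One condition needs checking: 9.1.1 does not say that the panel or the RT-PCR reports subtype, so the sponsor must confirm that typing can be obtained from them. Matching will not remove same-subtype community infections, including those acquired between discharge and the one-month visit; the quarantine-only sensitivity analysis addresses the latter.

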9.1.1 Viral Confirmation of Influenza Infection

BioFire Respiratory Panel. This CLIA-approved, commercially available molecular diagnostic test will be the primary means for determining influenza infection. The test result will be used for the day-to-day management and decision-making process for the care of study participants.

Cepheid 4-Plex. This CLIA-waived, commercially available molecular diagnostic test (which runs the Xpert® Xpress SARS-CoV-2/Flu/RSV assay) can be a satisfactory alternative means for determining influenza infection from the BioFire Respiratory Panel.

Qualitative RT-PCR. This research diagnostic test will be used as a secondary means for determining influenza infection. The test result may not be available for day-to-day decisions and the test may be performed in batched analysis.

Quantitative RT-PCR. This research diagnostic test will be used as another secondary means for the characterization of influenza infection. Peak viral shedding will be calculated for each subject as the maximum shedding during their CHIVITT participation period. Total viral shedding will be calculated with an area under the curve (AUC) with study day on the x-axis and shedding on the y-axis. The test result may not be available for day-to-day decisions and the test may be performed in batched analysis.

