6.1 General Outline of Activities During Each CHIVITT Cohort

The CHIVITT is to be conducted as a randomized, open, controlled study. Recipient participants for each cohort will enter the study hotel quarantine facility and be housed in individual hotel rooms. After a two-day run-in period to ensure that Recipients are free of preexisting respiratory infections *Exposure Events* will be held in a specially prepared event room.

Recipient participants of each cohort will be randomized to an intervention group or no intervention (Control Recipients, CR). Before entering their first *Exposure Event* each Intervention Recipients (IR) will be trained on how to comply with the intervention. IRs will be required to wear a lightweight plastic face shield, comply with hand hygiene (i.e., using a hand sanitization product every 15 minutes, plus periodic hand washing with soap and water), and avoid face touching during each planned *exposure event*. The face shield may only be removed after leaving the exposure room to go to the bathroom, for other short comfort breaks, and at mealtimes. In these instances, hand hygiene will be used after removing or replacing the face shield; and Donors will not be present. Hand washing with soap and water will be required before meals. IR will be separated from Donors by more than 6 feet during meals. The exposure room will be supervised by a trained member of the study staff who will monitor to ensure that Intervention Recipients wear the face shield continuously, are separated from Donors at meals, and do not touch their faces. Small sticks (e.g., coffee stirrers) will be provided to allow IRs to scratch their faces.

Exposure events are to occur as controlled (prescribed) activities within the exposure room. Exposure events will extend for up to 15 hours per day when Donors are available and able to participate (e.g., 15 hours 8am to 11pm). Each Recipient will participate in up to 60 hours of *Exposure Events* (e.g., 4 days at 15 hours/day) which may be spread over up to 9 or 10 days. During each *Exposure Event* multiple 1-3 hour group activities will be planned and supervised by trained members of the study staff. The group activities are intended to be entertaining and may consist of participating in a card game, board game, foosball game, karaoke, or other group activity which facilitates crowding, loud talking, etc. for potential influenza transmission.

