Should a recipient become laboratory-confirmed influenza infected (a countable SAR) and have accompanying symptoms during the CHIVITT, then the Recipient may be allowed to continue in the CHIVITT as a Donor. In order to accept the Recipient into the Donor status, the Donor informed consent form must be reviewed and signed by the participant. Recipients who are a countable SAR and do not want to continue in the CHIVITT may be safely discharged, contingent upon the absence of sufficient illness which may require treatment of influenza ([section 6.6](#)). However, once the 2 weeks have transpired, and if they have not become influenza infected, they will be allowed to end their participation in the CHIVITT. Recipients will also be allowed to withdraw from the study early, for their own personal reasons (see [section 6.7](#)).

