8.1.3 Daily Assessments

- Vital signs (including SpO₂, HR, RR, BP, and oral temperature) will be obtained at least twice daily (intended to be at least once in morning and once in afternoon). After the first two days, vital signs will be collected once a day until after exposure to a Donor or at PI discretion.
- A targeted physical examination may be performed, as directed by the medical history, medications, and vital signs assessment. An absence of significant past medical history, concomitant prescription medications, and abnormalities in vital signs will not require a physical examination.
- Once daily collection of a respiratory sample for viral quantitation and performance of a combined influenza and SARS-CoV-2 test (e.g., BioFire Respiratory Virus panel). After the

first two days of negative tests these daily assessments may be paused until after exposure to the first Donor.

- Twice daily completion of a Modified Jackson Score, Investigator Assessment Tool ([Appendix C](#)).
- Once daily completion of a self-reported Symptom Diary, FLU-PRO Survey Instrument and Validation Diary ([Appendix B](#)).
- Additional nasal swab and a saliva sample for research tests. However, these two samples will not be collected between the period after the incubation and before the first donor arrives.
- For Donors, Exhaled breath sampling

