8.1.5 Assessment within 48 hrs from Influenza Infection (Recipients)

Approximately 48 hrs (window 36-60 hrs) from virologic-confirmation of influenza infection (e.g., BioFire positive test), a blood volume of ~10 mL will be collected for the following safety labs: white blood cells (WBC), absolute lymphocyte count (ALC), hemoglobin (Hgb), platelets (PLT), alanine transaminase (ALT), and creatinine (Cr). The ALC is a variable under the Modified Jackson score. (see Appendix C for Score).

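### One molecular positive makes a countable secondary case, yet the swab has no fixed place relative to exposure and testing may be paused until after the first Donor contact

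*Protocol*

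**What the plan says.** **Counting rule.** Section 9.1 joins three criteria with an or: "The SAR of influenza infection will consist of virological confirmation, symptomatic infection, or serological evidence of an influenza infection". Within the virological criterion, section 9.1.1 says of the BioFire panel: "This CLIA-approved, commercially available molecular diagnostic test will be the primary means for determining influenza infection". The Cepheid assay "can be a satisfactory alternative means for determining influenza infection from the BioFire Respiratory Panel", so it is a substitute and not a confirmatory test. Of qualitative RT-PCR the section says: "This research diagnostic test will be used as a secondary means for determining influenza infection". Section 6.4 shows the rule in use: "Should a recipient become laboratory-confirmed influenza infected (a countable SAR". Section 8.1.5 times safety bloods "from virologic-confirmation of influenza infection (e.g., BioFire positive test".

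**Sampling.** Section 8.1.3 has one respiratory sample and panel test per day, with no time of day. After the "first two days of negative tests these daily assessments may be paused until after exposure to the first Donor". Appendix D, Recipient footnote 2, repeats this permission.

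**Exposure.** Section 6.1: "Exposure events will extend for up to 15 hours per day when Donors are available and able to participate". Sections 6.1 and 6.3 cap the total at 60 hours per Recipient.

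**Safeguards.** Section 4.1 excludes Recipients who test positive at admission. Section 6.1 adds a two-day run-in to screen out respiratory infection already present.

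**The concern.** The primary endpoint is meant to count infections passed from Donor to Recipient during exposure events. Three other things can produce a positive swab.

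- **An infection acquired before the first event.** If testing is paused until after first exposure, there may be no sample from just before exposure to show it.
- **Virus deposited in the nose without infection.** Face shields, hand hygiene, the no-face-touching rule and clean air all reduce deposition too. This error can therefore favour the intervention arms and resemble the effect under study.
- **Test error.** It accumulates over daily tests, is similar in all arms, and shrinks the observed effect.

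Because the criteria are joined by an or, a later negative RT-PCR or unchanged serology does not remove a case. By contrast, section 9.1.2 requires a repeat measurement to confirm fever and sets clock times for the symptom instruments. The swab has neither.

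**Working it through.** **1. The plan's own figures.** Section 9.2 gives a control SAR of 25%, reductions of 79% and 76%, and 84% power with 54 and 63 in an intervention group. The implied intervention SARs are 0.25 × 0.21 = 5.25% and 0.25 × 0.24 = 6.0%. A pooled two-proportion calculation with equal groups (an assumption, since the control number is not stated) gives 89.8% and 91.1% power one-sided at 5%, and 82.7% and 84.7% two-sided. The stated 84% is thus close to the two-sided values, although the text says one-sided. That is a separate matter. The protocol gives no specificity, false-positive rate or deposition rate, so steps 2 to 4 rest on assumed values.

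**2. Test error.** Assume k = 10 tests after first exposure (a stay of about 14 days less two run-in days allows about 12), independent errors, and specificity s.

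- False-case risk per uninfected Recipient: q = 1 − s^k.
- Observed risk in an arm with true risk p: p + (1 − p)q.

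| s | q | Control | Air hygiene | 79% shows as | Shield/hand | 76% shows as |
|---|---|---|---|---|---|---|
| 99.9% | 1.0% | 25.7% | 6.2% | 76% | 6.9% | 73% |
| 99.5% | 4.9% | 28.7% | 9.9% | 66% | 10.6% | 63% |

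For example, at 99.5%: 0.25 + 0.75 × 0.0489 = 0.2867; 0.0525 + 0.9475 × 0.0489 = 0.0988; 1 − 0.0988/0.2867 = 0.655. One-sided power falls from 89.8% to 87.9% (99.9%) or 80.3% (99.5%) for air hygiene, and from 91.1% to 89.5% or 82.5% for shield and hand hygiene.

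**3. Lower attack rates.** Section 2.1 records that the predecessor trial missed its planned attack rate. With q = 5%, the false share of counted cases is (1 − p)q / [p + (1 − p)q]. At p = 25% this is 0.0375/0.2875 = 13%; at p = 5% it is 0.0475/0.0975 = 49%.

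**4. Deposition that differs by arm.** As an illustration only, suppose there is no true effect, with a deposition-positive risk of 5% in controls and 0% under intervention. At a SAR of 25% the arms show 28.75% and 25%, an apparent reduction of 13%. One-sided rejection at a nominal 5% is then 11% to 12% for groups of 54 and 63. At a SAR of 5% it is 24% to 27%. With 5% against 1%, it is about 10% at a SAR of 25%.

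**5. Pre-exposure infection.** Section 2.5.1 puts incubation at 24 to 48 hours, and the run-in lasts two days, so the run-in only just spans the upper limit. Section 6.9 allows for late-onset, long-latency infection. Recipients enter near the local seasonal peak (section 6). Most infections acquired before admission should show by the end of the run-in. For a remaining one, the first sample after the pause may be post-exposure, and it would count.

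**The case against.** The one-positive rule is read from several sections together. Section 9.1.1 lists tests without giving a number of positives, section 8.1.5 is about bloods, and a statistical analysis plan might add detail. That is fair, but sections 9.1 and 6.4 do fix what counts, and no later plan can supply a pre-exposure swab that was never taken.

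Three stronger readings are tempting, and the documents do not support them.

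- **That incubating Recipients pass freely into exposure.** The admission exclusion, the two-day run-in, private rooms without guests (section 6.4) and air cleaning outside events (section 6.1) make this a residual risk.
- **That true and false cases cannot be told apart afterwards.** Serial swabs, saliva, quantitative RT-PCR, twice-daily symptom scores and one-month serology allow much of this. What cannot be recovered is the missing pre-exposure sample and the order of swab and event.
- **That the primary definition must require two positives.** This would lose sensitivity when cases are few. Sections 6.4 and 6.9 let infected Recipients leave early, so second samples may be missing. The symptom and serology criteria would still admit cases by the or rule.

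It is also true that contact is capped at 60 hours and that uninfected Recipients stay at least two days after their last event, so some swabs are free of same-day contact. At 99.9% specificity with little deposition, the whole effect is small.

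**Conclusion.** The point holds as a weakness in sampling order and case confirmation. It does not show that the endpoint is invalid. One molecular positive suffices for a case, the swab is not placed before or after that day's exposure, and the permitted pause can leave no sample from just before first exposure.

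Test error alone would turn the planned 79% reduction into about 76% to 66%, assuming 10 independent tests at 99.9% to 99.5% specificity. Deposition can push the other way because it can differ by arm, but its size is unknown. A reader might infer a known net bias towards or away from an effect; the documents support neither. False cases can occur, and how many cannot be derived from the protocol.

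**What to change.** 1. In section 8.1.3 and Appendix D, Recipient footnote 2, end the pause with a panel swab before the Recipient's first exposure event. State in section 9.1.1 that a positive on that swab is not a secondary case.
2. In section 8.1.3, collect the daily swab before that day's exposure event.
3. Keep the primary definition. Prespecify a sensitivity analysis that counts a virological case only if it is confirmed by a second positive sample on a later day or a titre rise of at least 4-fold, with type or subtype matching a Donor the Recipient met. A second specimen from the same day helps against test error but not against deposition, so it should not serve as confirmation.

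None of this changes clinical decisions, which can still follow the first positive.

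**Cost.** About one extra panel test per Recipient; the other samples are already collected. The protocol's example of a full day runs from 8 am to 11 pm and staff hours start at 8 am (sections 6.1 and 6.5), so pre-event swabbing needs an earlier start or a slightly later event.

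**Limits.** On such days a morning swab follows the previous event by about 9 hours, so deposition is reduced and not excluded. Recipients discharged early will lack a later-day sample, and the sensitivity analysis must rely on serology for them.
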